1. PROTOCOL SUMMARY

1.1 Schedule of Activities (SoA)

Schedule of activities in Phase 1 portion is described in [Table 1](#); schedule of activities in Phase 2 portion is described in [Table 2](#) and [Table 3](#).

Table 1 Schedule of Activities (Phase 1 portion)

	Screening ^a	Cycle 0		Cycle 1				Cycle 2	Cycle 3	Cycle 4	Cycle 5-12	Cycles 15, 18, 21 and \geq 24 ^b	EoT ^c	Safety Follow Up ^d	Post-treatment disease Follow up ^e	Survival Follow up ^f	Details in Section
		Single dose		Multiple doses													
Day of Each Cycle	-28 to -1	1	2	1	8	15	22	28	15	28	28	28	28				
Visit Window (Days)		0	0	0	± 2	± 2	± 2	± 2	± 2	± 2	± 2	± 2	± 3	+7	+7	± 7	± 7
Informed consent	X																Appendix A3
Hospitalization ^g		From Cycle 0 Day -1 to Cycle 0 Day 2															--
Inclusion/exclusion criteria	X																5.1 & 5.2
Routine clinical procedures																	
Demography	X																8
Medical history	X																8
B symptoms	X							X ^{dd}	X ^{dd}	X ^{dd}	X ^{dd}	Cycle 5, 6, 9 and 12 ^{dd}	Every 12W through Cycle 24, then every 24W thereafter ^{dd}				8.1.4

Table 1 Schedule of Activities (Phase 1 portion)

	Screening ^a	Cycle 0		Cycle 1				Cycle 2		Cycle 3	Cycle 4	Cycle 5-12		Cycles 15, 18, 21 and \geq 24 ^b	EoT ^c	Safety Follow Up ^d	Post-treatment disease Follow up ^e	Survival Follow up ^f	Details in Section
		Single dose		Multiple doses															
Day of Each Cycle	-28 to -1	1	2	1	8	15	22	28	15	28	28	28	28	28					
Visit Window (Days)		0	0	0	± 2	± 2	± 2	± 2	± 2	± 2	± 2	± 2	± 2	± 3	+7	+7	± 7	± 7	
Physical examination ^h	X	X	X	X	X	X	X	X	X	X	X	X	X	X	X	X	X		8.2.2
Vital signs ⁱ	X	X	X	X	X	X	X	X	X	X	X	X	X	X	X	X	X		8.2.3
ECOG status	X	X	X	X	X	X	X	X	X	X	X	X	X	X	X	X	X		8.2.5
ECG ^j	X	X			X		X		X	X	X	X	X	X	X	X	X		8.2.4
Concomitant treatments	←														→				6.5
Routine safety assessments																			
Pregnancy test ^k	X			X	As clinical indicated														8.1.3
Hematology ^l	X	X ^t		X	X	X	X	X	X	X	X	X	X	X	X	X	X		8.1.3
Clinical chemistry ^m	X	X ^t		X	X	X	X	X	X	X	X	X	X	X	X	X	X		8.1.3

Table 1 Schedule of Activities (Phase 1 portion)

	Screening ^a	Cycle 0		Cycle 1				Cycle 2		Cycle 3	Cycle 4	Cycle 5-12		Cycles 15, 18, 21 and ≥ 24 ^b	EoT ^c	Safety Follow Up ^d	Post-treatment disease Follow up ^e	Survival Follow up ^f	Details in Section
		Single dose		Multiple doses															
Day of Each Cycle	-28 to -1	1	2	1	8	15	22	28	15	28	28	28	28	28					
Visit Window (Days)		0	0	0	±2	±2	±2	±2	±2	±2	±2	±2	±2	±3	+7	+7	± 7	± 7	

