Abbreviations: ALT = alanine aminotransferase; AST = aspartate aminotransferase; CR = complete remission; CT = computed tomography; ECG = electrocardiogram; ECOG = Eastern Cooperative Oncology Group; EoT = End of Treatment; GI = gastrointestinal; HBV = hepatitis B virus; HCV = hepatitis C virus; HIV = human immunodeficiency virus; Ig = immunoglobulin; IHC = immunohistochemistry; Lab = laboratory; LDH = lactate dehydrogenase; LTFU = long-term follow-up; mos = months; NK cell = Natural killer cell; PCR = polymerase chain reaction; PET = positron emission tomography; PK = pharmacokinetic; PS = performance status.

Footnotes (Phase 1 portion)

- a. Screening tests should be performed within 28 days before the first administration of study drug, unless otherwise indicated.
- b. Treatment with acalabrutinib may be continued until disease progression or any other treatment discontinuation criterion is met. After Cycle 24, subjects will continue to have scheduled visits every 12 weeks (± 3 days) as outlined on the schedule of activities.
- c. End of treatment visit will be done for subjects who permanently discontinue study drug for any reason, including disease progression. (except for death, lost to follow up or withdrawal of consent). The EoT visit should be performed within 7 days of the last dose of study drugs, if possible, and is not required for subjects who discontinue from study treatment within 10 days of a scheduled study visit or if the EoT visit would be performed within 14 days of the SFU visit.
- d. 30 day (+ 7 days) safety follow-up visit is required for all subjects after his or her last dose of study drug to monitor for AEs, regardless of whether the subject receives a new anticancer therapy or demonstrates disease progression within this timeframe.
- e. Post-treatment Disease Follow up is only required for R/R MCL subjects, who discontinue from study treatment due to reasons other than disease progression. Subjects will be followed approximately every 12 weeks from the date of last disease evaluation until disease progression, regardless of whether the subject receives a new anticancer therapy.
- f. Survival Follow up is only applicable for R/R MCL subjects who progress, but have not withdrawn consent. Subjects will be contacted approximately every 12 weeks by clinical visit or telephone until death or lost to follow up to assess survival and the use of alternative anticancer therapy.

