- z. Acalabrutinib should be taken under fasting condition (at least 10 hours before dosing and at least 4 hours after dosing) in the Phase 1 portion morning dose of Cycle 0 Day 1 and Cycle 1 Day 8.
- aa. Adverse Events will be collected from time of signature of informed consent form until 30 days after the last dose of study treatment or the start of new anticancer therapy (whichever comes first). The safety follow-up period is defined as 30 (+7) days after study treatment is discontinued.
- bb. Survival status should be assessed at the time of the planned final analysis and additional milestone analyses as applicable.
- cc. Subjects will receive a drug diary to record the specific time each dose was taken and to record reasons for any missed doses. Subject compliance will be assessed at each study visit.
- dd. For R/R CLL subjects only.

Table 2 Schedule of Activities (Phase 2 Cohort A – R/R MCL)

	Screening ^a	Cycle 1					Cycle 2		Cycle 3	Cycle 4	Cycles 5-12	Cycles 15, 18, 21, ≥24 ^b	EoT ^c	Safety Follow Up ^c	Post-treatment disease Follow up ^d	Survival Follow up ^e	Details in Section
Day of Each Cycle	-28 to -1	1	8	15	22	28	15	28	28	28	28	28					
Visit Window (Days)		0	± 2					± 2	± 2	± 2	± 2	± 3	+ 7	+ 7	± 7	± 7	
Informed consent	x																Appendix A3
Inclusion/exclusion criteria	x																5.1 & 5.2
Routine clinical procedures																	
Demography	x																
Medical history	x																8
B symptoms	x																8.1.4
Physical examination ^f /Vital signs ^g	x	x	x	x	x	x	x	x	x	x	x	x	x	x			8.2.2 & 8.2.3
ECOG status	x	x	x	x	x	x	x	x	x	x	x	x	x	x			8.2.5
ECG ^h	x		x		x		x	x	x	x	x	x	x	x			8.2.4

Table 2 Schedule of Activities (Phase 2 Cohort A – R/R MCL)

	Screening ^a	Cycle 1					Cycle 2		Cycle 3	Cycle 4	Cycles 5-12	Cycles 15, 18, 21, ≥24 ^b	EoT ^c	Safety Follow Up ^c	Post-treatment disease Follow up ^d	Survival Follow up ^e	Details in Section
Day of Each Cycle	-28 to -1	1	8	15	22	28	15	28	28	28	28	28					
Visit Window (Days)		0	± 2					± 2	± 2	± 2	± 2	± 3	+ 7	+ 7	± 7	± 7	
Concomitant medications		←											→				6.5
Routine safety assessments																	
Pregnancy test ⁱ	X	x	As clinically indicated														8.1.3
Hematology ^j	X	x ^r	x	x	x	x	x	x	x	x	x	x	x	x	x		8.1.3
Clinical chemistry ^k	X	x ^r	x	x	x	x	x	x	x	x	x	x	x	x	x		8.1.3
Hepatitis and HIV serology ^o	X																8.1.3

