long-term follow-up; mos = months; NK cell=Natural killer cell; PCR = polymerase chain reaction; PET = positron-emission tomography; PK = pharmacokinetic; PS= performance status.

Footnotes (Phase 2- cohort A)

- a. Screening tests should be performed within 28 days before the first administration of study drug, unless otherwise indicated.
- b. Treatment with acalabrutinib may be continued until disease progression or any other treatment discontinuation criterion is met. After Cycle 24, subjects will continue to have scheduled visits every 12 weeks (± 3 days) as outlined on the schedule of activities.
- c. End of treatment visit will be done for subjects who permanently discontinue study drug early for any reason, including disease progression (except for death, lost to follow up or withdrawal of consent). The EoT visit should be performed within 7 days of the last dose of study drugs, if possible, and is not required for subjects who discontinue from study treatment within 10 days of a scheduled study visit or if the EoT visit would be performed within 14 days of the SFU visit. In addition, a 30 day (+ 7 days) safety follow-up visit is required for all subjects after his or her last dose of study drug to monitor for AEs, regardless of whether the subject receives a new anticancer therapy or demonstrates disease progression within this timeframe.
- d. Post-treatment Disease Follow up visit will be done for subjects who discontinue from study treatment due to reasons other than disease progression. Subjects will be followed approximately every 12 weeks from the date of last disease evaluation until disease progression, regardless of whether the subject receives a new anticancer therapy.
- e. Survival follow up visit will be done for subjects who progress but have not withdrawn consent. Subjects will be contacted approximately every 12 weeks by clinical visit or telephone until death or lost to follow up to assess survival and the use of alternative anticancer therapy
- f. The physical examination includes height (Screening only) and weight, and examination of the skin, eyes, ears, nose, throat, lungs, heart, abdomen, extremities, musculoskeletal, nervous, lymphatic system, and general appearance. The lymphatic system examination will include examination of palpable lymph nodes and spleen and liver below the costal margin on the respective side.

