- d. Each subject should be followed until disease progression. If disease progression has not occurred at the time of the 30-day SFU visit, post-treatment disease follow-up visits should occur approximately every 3 months (12 weeks) from the date of last disease evaluation until disease progression, regardless of whether the subject receives a new anticancer therapy.
- e. Once subjects progress, for all subjects who have not withdrawn consent, they will be contacted approximately every 3 months (12 weeks) by clinic visit or telephone, to assess survival and use of alternative anticancer therapy until death or lost to follow-up.
- f. Vital signs (blood pressure, pulse rate, and body temperature) should be assessed after at least 5 minutes of rest for the subject in a quiet setting without distractions (e.g., television, cell phones).
- g. Twelve-lead ECGs will be obtained after the subject has been resting supine for at least 10 minutes before study-related ECGs.
- h. Women of childbearing potential only. A urine or serum pregnancy test is acceptable. Pregnancy testing can be done more frequently than the protocol-defined schedule.
- i. Hepatitis and HIV serology must include hepatitis B surface antigen (HBsAg), hepatitis B surface antibody (anti-HBs), hepatitis B core antibody (anti-HBc), hepatitis C (HCV) antibody, and HIV antibody.
- j. Subjects who are anti-HBc positive, HBsAg negative should have a quantitative PCR test for HBV DNA performed during screening and every month during treatment Cycle 2 through 19. After Cycle 19, monitoring will occur every 3 months. HBV monitoring should continue until 12 months after last dose of study drug(s). Any subject with a rising viral load (above lower limit of detection) should discontinue study drug and have antiviral therapy instituted and a consultation with a physician with expertise in managing hepatitis B. As intravenous immunoglobulins (IVIG) may cause false positive hepatitis serology, PCR testing monthly is not required in subjects who are currently receiving or received prophylactic IVIG within 3 months before study enrolment and have a documented negative anti-HBc test before the initiation of IVIG therapy. PCR testing should be performed when clinically indicated (e.g., in the setting of rising transaminase levels).

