4.2.3. Safety analyses

4.2.3.1. General considerations for safety

The analysis will be performed separately for all three cohorts: all phase 1 patients, R/R MCL patients (phase 1 and phase 2 combined) and phase 2 R/R CLL patients except where it is mentioned otherwise.

Time windows will be defined for any presentations that summarize values by visit. The following conventions will apply:

- The time windows will be exhaustive so that data recorded at any time point has the potential to be summarized. Inclusion within the time window will be based on the actual date and not the intended date of the visit.
- All unscheduled visit data have the potential to be included in the summaries.
- The window for the visits following baseline will be constructed in such a way that the upper limit of the interval falls half way between the two visits (the lower limit of the first post-baseline visit will be Day 2). If an even number of days exists between two consecutive visits then the upper limit will be taken as the midpoint value minus 1 day. For example, the visit windows for vital signs data (with 1 weeks between scheduled assessments) are:
 - Day 8, visit window 2 – 11
 - Day 15, visit window 12 – 18
 - Day 22, visit window 19 – 25
 - Day 28, visit window 26 – 32
- For summaries showing the maximum or minimum values, the maximum/minimum value recorded on treatment will be used (regardless of where it falls in an interval).
- Listings should display all values contributing to a time point for a patient.
- For visit based summaries
 - If there is more than one value per patient within a time window then the closest value to the scheduled visit date will be summarized, or the earlier, in the event the values are equidistant from the nominal visit date. The listings will highlight the value for the patient that contributed to the summary table, wherever feasible. Note: in summaries of extreme values all post baseline values collected are used including those collected at unscheduled visits regardless of whether or not the value is closest to the scheduled visit date
- For summaries at a patient level, all values will be included, regardless of whether they appear in a corresponding visit based summary, when deriving a patient level statistic such as a maximum.

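### SAP 4.2.3.1 sets no treatment-period limit on laboratory data, so off-drug hematology (and chemistry in MCL) enters by-visit summaries, and its two extreme-value rules conflict

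*Protocol*

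**What the plan says.** **Visits.** Protocol 1.1, Table 2 footnote d, follows Cohort A subjects who stop for reasons other than progression about every 12 weeks "until disease progression, regardless of whether the subject receives a new anticancer therapy". Table 1 footnote e has the same rule but a narrower scope: "Post-treatment Disease Follow up is only required for R/R MCL subjects". Table 3 footnote d, for Cohort B, says "post-treatment disease follow-up visits should occur approximately every 3 months (12 weeks) from the date of last disease evaluation until disease progression", again whether or not a new therapy has started. Protocol 7.1.2 gives the interval as 12 or 24 weeks.

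**Windows.** SAP 4.2.3.1 governs every summary by visit: "The time windows will be exhaustive so that data recorded at any time point has the potential to be summarized". A value is placed by its actual date, and unscheduled values are eligible. No bullet excludes values after the last dose or after new therapy.

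**Extreme values.** One bullet of SAP 4.2.3.1 says that "the maximum/minimum value recorded on treatment will be used". A later note in the same list says that "in summaries of extreme values all post baseline values collected are used".

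**Adverse events, for contrast.** SAP 3.2.2.1 ends the treatment-emergent period for adverse events 30 days after the last dose, or at new anticancer therapy if that is earlier. No such period is stated for laboratory data.

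**The concern.** Laboratory data are a safety endpoint in Phase 1 and in both Phase 2 cohorts. A blood count or transaminase taken after acalabrutinib has stopped, possibly under another regimen, says little about acalabrutinib. If the window rule is followed as written, such a value is reported as the Cycle 9 or Cycle 12 result alongside values from subjects still on drug. Where worst values are tabulated, two programmers could follow different sentences of the same section and produce different tables. In Cohort B, a fall in lymphocyte count caused by the next regimen could be recorded as resolution of lymphocytosis on acalabrutinib.

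**Working it through.** The plan states no figure on this point to reproduce. The check compares the schedules with the window rule.

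**1. Which tests are marked at post-treatment disease follow-up** (cells counted back from the right-hand section column):
- Table 1: hematology and chemistry are marked, for R/R MCL subjects only. The coagulation and urinalysis rows are one cell short in the extracted text, so I do not rely on them.
- Table 2: hematology and chemistry each carry 15 marks across 16 visit columns, against 14 for physical examination and vital signs, which end at safety follow-up. The 15th mark is post-treatment disease follow-up. Coagulation and urinalysis are also marked there.
- Table 3: hematology is marked. Serum immunoglobulins and T/B/NK counts continue every 24 weeks. Chemistry, coagulation and urinalysis end at safety follow-up, as the adverse event row does.

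**2. Where those visits fall in study time.** A post-treatment visit occurs 12 weeks (84 days) after the last disease evaluation.
- Cohort A: Cycle n Day 28 is study day 28n. Last evaluation at Cycle 6 Day 28 is day 168; 168 + 84 = 252 = 28 × 9, which is Cycle 9 Day 28. The next visit is 252 + 84 = 336 = 28 × 12, Cycle 12 Day 28.
- Cohort B: Cycle n Day 1 is study day 28(n − 1) + 1. Last evaluation at Cycle 7 Day 1 is day 169; 169 + 84 = 253 = 28 × 9 + 1, which is Cycle 10 Day 1.

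These off-drug samples fall on the nominal days of on-drug visits. Exhaustive, date-based windows accept them, and no other rule removes them.

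**3. What limit each output in SAP 4.2.3.4 carries:**
- Summaries by scheduled study day: none.
- Shift to worst CTCAE grade: on-treatment, with no period defined.
- Counts of abnormal results, all grades and grade 3 or higher: treatment-emergent, not defined for laboratory data.
- Shifts to maximum and minimum value, and the urinalysis shift: only the two conflicting rules in 4.2.3.1.
- Liver-test category counts: none.
- Scatter plots of maximum ALT or AST against bilirubin: treatment-emergent, not defined.
- CLL lymphocytosis: peak uses any post-baseline lymphocyte count, and resolution is the first later value meeting the criterion. Neither is limited to treatment.
- Potential Hy's Law listing flag: deliberately the whole study.

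**4. Scale per subject.** The pooled MCL group lies between 33 (no Phase 1 subject has MCL) and 45 (33 + 12, all of them do). One subject crossing a liver-test threshold only after stopping would move that category by 1/45 = 2.2 to 1/33 = 3.0 percentage points. In Cohort B one subject is 1/60 = 1.7 points. For a late by-visit window, assume 20 subjects on drug and 1 to 4 off drug: the off-drug share is 1/21 = 4.8% to 4/24 = 16.7%. These inputs are assumptions that show sensitivity; they are not estimates.

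**The case against.** The best defence is that the SAP already restricts much of this. CTCAE-grade shifts are on-treatment, and abnormality counts and liver scatter plots are treatment-emergent. The note on all post-baseline values sits under the rule for picking the closest value in a window. It may mean only that unscheduled and non-closest values count when an extreme is sought. That reading is plausible and probably intended, but the text does not say that the on-treatment bullet still governs, and on-treatment has no end date for laboratory data under either reading.

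Table 3 hematology is listed under response evaluation because iwCLL assessment needs blood counts. That explains why it is collected. It does not keep it out of the safety tables: SAP Table 4 and 4.2.3.4 treat hematology as a safety laboratory variable, and 3.3.2 applies the same variables to Phase 2.

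Three stronger readings should be resisted:
- A reader might infer that all three schedules keep the full safety panel running. Table 3 does not, and Table 1 does so only for MCL subjects.
- A reader might infer that grade 3 or higher laboratory rates are inflated by 2.2 to 9.1 points (1/45 to 3/33). That table is already limited to treatment-emergent results, and the one to three events are assumed.
- A reader might infer that any mismatch between laboratory and adverse event rates shows the problem. Protocol 8.3.7 records deterioration in mandated tests as an adverse event only if it is serious or leads to discontinuation (associated symptoms are reported separately), so the two differ by design.

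It also stands that safety data are descriptive, with no formal test at risk.

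**Conclusion.** The concern holds in a bounded form. By-visit laboratory summaries, as specified, mix on-drug and off-drug values: hematology and chemistry for MCL, and hematology plus the 24-weekly immune tests for Cohort B. The minimum and maximum value shifts, the urinalysis shift, the liver-test categories and the lymphocytosis analyses have no clear limit. The CTCAE-grade shifts and abnormality counts have a stated limit whose period is undefined. The documents do not support saying that the SAP directs off-drug extremes into every laboratory table.

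Only subjects who stop without progression contribute, and their number cannot be derived from the documents. The conclusion rests on the column positions in Tables 1 to 3. These are secure for Table 2 hematology and chemistry, whose rows are complete, and less secure for Table 2 urinalysis, whose Cycle 1 mark appears displaced. This is worth correcting before the tables are programmed; it does not affect the efficacy conclusions.

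**What to change.** In SAP 4.2.3.1, define the on-treatment period for laboratory safety data as first dose to the earlier of 30 days after last dose and start of new anticancer therapy, which is the window already in SAP 3.2.2.1. Use the same period to define a treatment-emergent laboratory abnormality. Apply it to the by-visit, minimum/maximum, shift, abnormality and liver-category summaries and to the lymphocytosis analyses. Reword the note on extreme values to cover all on-treatment post-baseline values, including unscheduled ones. Keep later values in the listings with a flag.

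Leave potential Hy's Law identification and counts open for the whole study, as Protocol Appendix D and SAP 4.2.3.4 have it, and flag events after the window. A blanket restriction of the liver tables would contradict that definition.

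The cost is SAP wording and one derived flag; no visit or procedure changes. The small downside is that late abnormalities other than potential Hy's Law appear only in listings.

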1.2 Synopsis

National coordinating investigator:

PPD

[figure not shown]
Beijing City,

China.

Protocol Title: A Phase 1/2 Open Label, Multi-center Study to Assess the Safety, Tolerability, Pharmacokinetics and Clinical Efficacy of Acalabrutinib in Chinese Adult Subjects with Relapsed or Refractory Mantle Cell Lymphoma, Chronic Lymphocytic Leukemia or other B-cell Malignancies.

Rationale

CCI

Overall design

This is an open-label, two-part study to assess the safety, tolerability, pharmacokinetics and clinical efficacy of acalabrutinib in Chinese adult subjects with R/R MCL, R/R CLL or other B-cell malignancies. The study is divided into 2 parts: Phase 1 portion and Phase 2 portion.

Phase 1 portion

The primary objective of Phase 1 portion is to assess the safety, tolerability and pharmacokinetics of acalabrutinib in Chinese subjects with R/R B-cell malignancies and the secondary objective is to access the efficacy of acalabrutinib in Chinese subjects with R/R B-cell malignancies. Approximately 12 subjects will be enrolled in the Phase 1 portion. The study population includes subjects with R/R non-GCB diffuse large B-cell lymphoma (DLBCL), follicular lymphoma (FL), mantle cell lymphoma (MCL), chronic lymphocytic leukemia (CLL), small lymphocytic lymphoma (SLL).

Subjects will be administered a single dose of acalabrutinib 100 mg at Cycle 0 Day 1. During the following 2 days wash-out period, intensive PK samples will be collected before and after the first dose until pre-dose at Cycle 1 Day 1. From Cycle 1 Day 1, subjects will be administered multiple doses of acalabrutinib 100 mg BID on a continuous schedule (28 days per cycle). Intensive PK samples will be collected on Cycle 1 Day 8 for 12-hour PK profile at steady state. Additional sparse PK samples will be collected on Cycle 1 Day 28 to assess time-

dependent changes. Treatment with acalabrutinib may be continued for Cycle 2 onwards until disease progression or any other treatment discontinuation criterion is met. All subjects who discontinue the study drug will have a safety follow-up visit 30 (+7) days after the last dose of study drug.

The dose regimen of multiple doses of 100 mg BID has been found to be safe/tolerable and effective in overseas clinical studies in Western and Asian subjects. In case of intolerable toxicity, dose reduction to 100 mg QD may be considered (details in Section [6.6.2](#)).

Phase 2 portion

Phase 2 portion is to further evaluate clinical efficacy, safety and tolerability of acalabrutinib in subjects with R/R MCL and R/R CLL. The enrolment of Phase 2 portion will be initiated per Safety Review Committee (SRC) recommendation based on preliminary safety data from Phase 1 portion. Detailed information will be provided in SRC charter. Evaluation of efficacy and safety will be performed independently for each cohort.

Cohort A

Cohort A is to evaluate clinical efficacy, safety and tolerability in subjects with pathologically documented MCL who have relapsed after or were refractory to ≥ 1 (but not >5) prior treatment regimens. Approximately 33 R/R MCL subjects will be enrolled to receive 100 mg of acalabrutinib BID in repeated 28-day cycles.

Cohort B

Cohort B is to evaluate clinical efficacy, safety and tolerability in subjects with CLL who have failed from ≥ 1 prior systemic therapies. Approximately 60 R/R CLL subjects will be enrolled to receive 100 mg of acalabrutinib BID in repeated 28-day cycles.

Treatment with acalabrutinib may be continued until disease progression or any other treatment discontinuation criterion is met. Dose modification provisions are outlined in Section [6.6.2](#). Note: Temporary withholding of study drug for as little as 7 days can cause a transient worsening of disease and/or of constitutional symptoms. Refer to Section [7.1](#) for more information on assessing disease progression under these circumstances. An early termination visit is required for any subjects who permanently discontinue study drug for any reason (except for death, lost to follow up or withdrawal of consent), including disease progression. In addition to the early termination visit, all subjects who discontinue study drug will have a safety follow-up visit 30 (+ 7) days after his or her last dose of study drug.

All subjects will have hematology, clinical chemistry, and urinalysis safety panels done at screening. Once dosing commences (Cycle 1 Day 1), all subjects will be evaluated for safety, including hematology and clinical chemistry at regular basis.

Tumor assessments for R/R MCL subjects will be performed at 8- to 12-week intervals throughout the study. Tumor assessments for R/R CLL subjects will be performed at 12- to 24-week intervals throughout the study.

Refer to Section 1.1 for a comprehensive list of study assessments and their timing. The end of trial is defined as the 3rd analyses for R/R CLL subjects of Phase 2 cohort B, which will occur approximately 24 months after the last R/R CLL subject enrolled into Phase 2.

The primary efficacy analysis (R/R MCL and R/R CLL subjects) will be based on Independent Review Committee assessment.

Objectives and Endpoints	
Phase 1 Portion - Primary Objective:	Endpoint/Variable:
To assess the safety and tolerability of acalabrutinib in Chinese subjects with R/R B-cell malignancies	AEs, laboratory data, vital signs, and ECGs
To characterize pharmacokinetics of acalabrutinib and its major metabolite (ACP-5862) in Chinese subjects with R/R B-cell malignancies	AUC _{inf} , AUC ₀₋₁₂ , AUClast, C _{max} , t _{max} , CL/F (acalabrutinib only), V _z /F (acalabrutinib only), λ _z , t _{1/2} λ _z , Metabolite: Parent ratio (C _{max}), and Metabolite: Parent ratio (AUC) after single dose; AUC _τ , C _{max} , C _{min} , t _{max} , CL/F (acalabrutinib only), Metabolite: Parent ratio (C _{max}), Metabolite: Parent ratio (AUC _τ), TCP, Rac AUC and Rac C _{max} after multiple doses
Phase 1 Portion - Secondary Objective:	Endpoint/Variable:
To assess the efficacy of acalabrutinib in Chinese subjects with R/R B-cell malignancies	For R/R CLL: Tumor response (number of patients with CR, CRI, PR, nPR, PRL, SD, PD) For other R/R B-cell malignancies: Tumor response (number of patients with CR, PR, SD, PD)
Phase 2 Portion Cohort A - Primary Objective:	Endpoint/Variable:
To assess the efficacy of acalabrutinib in Chinese subjects with R/R MCL	ORR as assessed by BICR per Lugano classification for NHL (Cheson 2014)
Phase 2 Portion Cohort A- Secondary Objective:	Endpoint/Variable:
To further assess the efficacy of acalabrutinib in Chinese subjects with R/R MCL	DoR, PFS and TTR as assessed by BICR per Lugano classification for NHL (Cheson 2014); ORR, DoR, PFS and TTR as assessed by investigators per Lugano classification for NHL (Cheson 2014); OS
To assess the safety profile of acalabrutinib in Chinese subjects with R/R MCL	AEs, laboratory parameters, vital signs, and ECGs
To assess pharmacokinetics of acalabrutinib in Chinese subjects with R/R MCL	Plasma concentration of acalabrutinib (sparse sampling)

Objectives and Endpoints	
Phase 2 Portion Cohort B- Primary Objective:	Endpoint/Variable:
To assess the efficacy of acalabrutinib in Chinese subjects with R/R CLL	ORR as assessed by BICR per iwCLL 2018 criteria
Phase 2 Portion Cohort B- Secondary Objective:	Endpoint/Variable:
To further assess the efficacy of acalabrutinib in Chinese subjects with R/R CLL	DoR, PFS and TTR as assessed by BICR per iwCLL 2018 criteria; ORR, DoR, PFS and TTR as assessed by investigators per iwCLL 2018 criteria; TTNT; CCI [REDACTED]
To assess the safety profile of acalabrutinib in Chinese subjects with R/R CLL	AEs, laboratory parameters, vital signs, and ECGs
To assess pharmacokinetics of acalabrutinib in Chinese subjects with R/R CLL	Plasma concentration of acalabrutinib (sparse sampling)
Safety Objectives are contained within the primary and secondary objectives.	

Data from R/R MCL subjects in both Phase 1 and Phase 2 will be combined for analysis.

Study Period

Study period		Phase of development
Estimated date of first subject enrolled	Q2, 2020	Phase 1 portion
Estimated date of last subject completed Phase 1 portion	Q2, 2022	Phase 1 portion
Estimated date of first subject enrolled Phase 2 portion	Q3, 2020	Phase 2 portion
Estimated date of last subject completed Phase 2 portion	Q4, 2023	Phase 2 portion

Number of Subjects

Approximately 12 Chinese subjects with R/R B-cell malignancies will be enrolled in Phase 1 portion. Approximately 33 Chinese subjects with R/R MCL (cohort A) and 60 Chinese subjects with R/R CLL (cohort B) will be enrolled in Phase 2 portion.

Treatments and treatment duration

In Phase 1 portion, all eligible subjects will first receive a single dose of acalabrutinib 100 mg and after 2 days washout period, the subjects will start to be treated at a continuous dosing of

[figure not shown]
acalabrutinib twice daily until disease progression or any other treatment discontinuation criteria is met.

In Phase 2 portion, all eligible subjects will be treated at a continuous dosing of acalabrutinib 100 mg BID until disease progression or any other treatment discontinuation criterion is met.

[figure not shown]
Statistical methods

Approximately 12 subjects will be enrolled in Phase 1 portion. Additional subjects may be enrolled to ensure at least 8 eligible subjects with evaluable single- and multiple-dose PK profiles based on China regulatory recommendations. Approximately 93 subjects will be enrolled in Phase 2 portion (33 subjects with R/R MCL in cohort A and 60 subjects with R/R CLL in cohort B). A sample size of 33 subjects with R/R MCL (cohort A) will provide a 95% two-sided confidence interval centred around an expected ORR of 80% that excludes an ORR of 60% as a lower bound. With 60 subjects from R/R CLL (cohort B), an exact binomial test with a nominal one-sided 2.5% significance level will have 90% power to detect the difference between a null hypothesis ORR of 70% and an alternative ORR of 88%.

CCI

CCI

All subjects who receive at least one dose of acalabrutinib will be included in safety analysis set and used for safety reporting. Safety data will not be formally analyzed. The number and percent of subjects with treatment-emergent adverse events (TEAEs) will be summarized. Summary of other safety parameters will be provided where appropriate. The safety summaries will be produced for Phase 1 and Phase 2 portion, separately. As for Phase 2 portion, safety parameters will be summarized by each cohort.

All subjects who received at least one dose of acalabrutinib and for whom baseline tumor assessment is available will be included in tumor response set and used for efficacy analyses. Regarding anti-tumor assessment, data from R/R MCL subjects in both Phase 1 and Phase 2 will be combined for analysis. Whereas, efficacy analysis of tumor response in R/R CLL will

only be applied for R/R CLL subjects in Phase 2. ORR with corresponding 95% exact CIs will be presented by each cohort.

There are two planned analyses for all subjects of Phase 1 portion and cohort A of Phase 2 portion.

The data cut-off for 1st analysis will take place when both of the following two conditions are met

- Approximately 1 month after Cycle 1 day 1 of the last subject in Phase 1 to allow required PK samplings at cycle 0 and cycle 1 are collected.
- Approximately 6 months after last R/R MCL subjects in across both Phase 1 and Phase 2 to allow a minimum of two tumor assessments after first dose.

A Clinical Study Report will be prepared to summarize PK, safety and efficacy data for Phase 1 portion and/or cohort A of Phase 2 portion. R/R MCL subjects in Phase 1, if applicable, will be combined together with the subjects in cohort A of Phase 2 portion for MCL analysis.

The data cut-off for 2nd analysis will take place approximately 14 months after last subject enrolled in both Phase 1 and cohort A of Phase 2. A Clinical Study Report Addendum including all subjects of Phase 1 portion and/or cohort A of Phase 2 portion will be prepared at that time.

There are three planned analyses for R/R CLL subjects of cohort B of Phase 2 portion.

The data cut-off for 1st analysis will take place when approximately 6 months after last R/R CLL subjects enrolled in Phase 2. A Clinical Study Report will be prepared to summarize efficacy, safety and PK data for cohort B of Phase 2 portion. Efficacy analysis of tumor response in R/R CLL will only be applied for R/R CLL subjects in Phase 2. Tumor response of R/R CLL subjects in Phase 1 may be listed separately in a proper way.

[figure not shown]
The data cut-off for 2nd analysis will take place when approximately 12 months after last R/R CLL subject enrolled in Phase 2. A Clinical Study Report Addendum including R/R CLL subjects of cohort B of Phase 2 portion will be prepared at that time.

The data cut-off for 3rd analysis will take place approximately 24 months after last R/R CLL subject enrolled in Phase 2. A Clinical Study Report Addendum including R/R CLL subjects of cohort B of Phase 2 portion will be prepared at that time.

